### Efficacy Endpoints

Disease response will be assessed via revised Lugano classification for the response assessment of Hodgkin and non-Hodgkin lymphoma. The end of treatment assessment is determined by positron emission tomography (PET)-computed tomography (CT) imaging for patients with fluoro-deoxyglucose (FDG) avid hematologic malignancies. Responses are designated, complete response (CR), partial response (PR) stable disease (SD) or progressive disease (PD). For disease histologies with low or variable FDG avidity, CT based response will be utilized. Disease response will be divided into local and systemic response and will be determined beginning at 3 months after treatment initiation.

#### 4.2.2.1 Biomarker Research

Blood samples and tumor biopsies will be obtained from consenting patients at baseline and/or on treatment from subjects enrolled on the study at the indicated time points shown in the Trial Flow Chart under Section 6.0. The overall goal of the biomarker studies is to identify predictive, surrogate, mechanistic, and pharmacodynamic biomarkers of pembrolizumab and EBRT combination therapy. Peripheral blood mononuclear cells (PBMC) and serum will be isolated from blood samples and cryopreserved for batched analysis.

PBMC samples will be analyzed by up to 10-color multiparametric flow cytometry to determine alteration in effector and regulatory T cell subsets and to determine expression of various co-stimulatory and co-inhibitory receptors on T cells. Serum samples will be analyzed for alteration in various cytokines and chemokines. Tumor biopsies will be analyzed by whole genome gene expression profiling (GEP), immunohistochemistry (IHC), and/or flow cytometry. Immunohistochemical and flow cytometric analyses will be performed on baseline tumor biopsy specimens to evaluate for baseline levels of PD-L1, PD-1, CD4+ and CD8+ Tumor Infiltrating Lymphocytes (TILs) and regulatory T cells (Tregs) within the tumor. Gene expression profiling will also be performed on baseline tumor biopsy samples. We will also assess the predictive significance of the intra-tumoral effector T cell gene signature that was associated with clinical outcome in follicular lymphoma patients treated with rituximab plus pidilizumab therapy that was recently described by us. The same analyses will be conducted on tumor biopsy samples obtained post-RT. Immunophenotyping via flow cytometry will be performed on peripheral blood mononuclear cells obtained from baseline and serial post-treatment samples to determine alteration in effector and regulatory T cell subsets and to determine expression of various co-stimulatory and co-inhibitory receptors on T cells.

## 5.0 METHODOLOGY

### 5.1 Entry Criteria

#### 5.1.1 Diagnosis/Condition for Entry into the Trial

Male or female subjects with histologic evidence of aggressive Non-Hodgkin lymphoma (NHL) who have relapsed or progressive disease after 2 prior systemic therapies (including autologous stem cell transplant) or have relapsed/refractory disease and are no longer candidates for cytotoxic chemotherapy are eligible for this study.

#### 5.1.2 Subject Inclusion Criteria

In order to be eligible for participation in this trial, the subject must:

1. Have at least one site of lymphomatous disease amenable to external beam radiation therapy (EBRT)
2. Have pathologic confirmation of aggressive Non-Hodgkin Lymphoma (including diffuse large B cell lymphoma, transformed follicular lymphoma, transformed marginal zone lymphoma, primary mediastinal B-cell lymphoma, T cell lymphoma and NK T-cell lymphoma). Patients with indolent B cell lymphoma are excluded.
3. Be willing and able to provide written informed consent/assent for the trial.
4. Be  $\geq 18$  years of age on day of signing informed consent.
5. Have measurable disease ( $\geq 1.5$  cm in the longest diameter for nodal or extranodal disease)
6. Have provided archival tumor tissue sample or newly obtained core or excisional biopsy of a tumor lesion not previously irradiated. Formalin-fixed, paraffin embedded (FFPE) tissue blocks are preferred to slides. *Newly obtained* biopsies are preferred to *archived* tissue. *Newly-obtained is defined as a specimen obtained up to 6 weeks (42 days) prior to initiation of treatment on Day 1. Subjects for whom newly-obtained samples cannot be provided (e.g. inaccessible or subject safety concern) may submit an archived specimen.* Note: If submitting unstained cut slides, newly cut slides should be submitted to the testing laboratory within 14 days from the date slides are cut.
7. Have an Eastern Cooperative Oncology Group (ECOG) performance status of 0 to 1. Evaluation of ECOG is to be performed within 7 days prior to the date of allocation/randomization.
8. Demonstrate adequate organ function as defined in Table 1, all screening labs should be performed within 10 days of treatment initiation.

Table 1 Adequate Organ Function Laboratory Values

System	Laboratory Value
--------	------------------

Hematological	
Absolute neutrophil count (ANC)	$\geq 1,000 / \text{mcL}$
Platelets	$\geq 50,000 / \text{mcL}$
Hemoglobin	$\geq 8 \text{ g/dL}$ or $\geq 5.6 \text{ mmol/L}$ without transfusion or EPO dependency (within 7 days of assessment)
Renal	
Serum creatinine OR Measured or calculated a creatinine clearance (GFR can also be used in place of creatinine or CrCl)	$\leq 1.5 \times \text{upper limit of normal (ULN)}$ OR $\geq 60 \text{ mL/min}$ for subject with creatinine levels $> 1.5 \times$ institutional ULN
Hepatic	
Serum total bilirubin	$\leq 1.5 \times \text{ULN}$ OR Direct bilirubin $\leq \text{ULN}$ for subjects with total bilirubin levels $> 1.5 \text{ ULN}$
AST (SGOT) and ALT (SGPT)	$\leq 2.5 \times \text{ULN}$ OR $\leq 5 \text{ ULN}$ for subjects with liver metastases
Albumin	$\geq 2.5 \text{ mg/dL}$
Coagulation	
International Normalized Ratio (INR) or Prothrombin Time (PT)	$\leq 1.5 \times \text{ULN}$ unless subject is receiving anticoagulant therapy as long as PT or PTT is within therapeutic range of intended use of anticoagulants
Activated Partial Thromboplastin Time (aPTT)	$\leq 1.5 \times \text{ULN}$ unless subject is receiving anticoagulant therapy as long as PT or PTT is within therapeutic range of intended use of anticoagulants

aCreatinine clearance should be calculated per institutional standard.

- Female subject of childbearing potential should have a negative urine or serum pregnancy within 72 hours prior to receiving the first dose of study medication. If the urine test is positive or cannot be confirmed as negative, a serum pregnancy test will be required.
- Female subjects of childbearing potential (Section 5.7.2) must be willing to use an adequate method of contraception as outlined in Section 5.7.2 – Contraception, for the course of the study through 120 days, corresponding to time needed to eliminate any Merck study treatment(s) and/or any active comparator/combination, plus 30 days (a menstruation cycle) for study treatments with risk of genotoxicity after the last dose of study medication.

Note: Abstinence is acceptable if this is the usual lifestyle and preferred contraception for the subject.

- A male participant must agree to use a contraception as detailed in Appendix 3 of this protocol during the treatment period and for at least the entire period during which the male participant receives the study drug pembrolizumab, corresponding to time needed to eliminate any Merck study treatment(s) and/or any active comparator/combination, plus an additional 120 days (a spermatogenesis cycle) for study treatments with evidence of genotoxicity at any dose, after the last dose of study treatment and refrain from donating sperm during this period.

Note: Abstinence is acceptable if this is the usual lifestyle and preferred contraception for the subject.

### 5.1.3 Subject Exclusion Criteria

The subject must be excluded from participating in the trial if the subject:

1. Has had prior radiation therapy to the potential radiation target such that additional radiation therapy is considered unsafe by the treating radiation oncologist
2. Has a history of allogeneic stem cell transplantation.
3. Has a diagnosis of active scleroderma or lupus or any other autoimmune disease that by the opinion of the treating radiation oncologist would put the patient at unacceptable risk of toxicity.
4. Is currently participating and receiving study therapy or has participated in a study of an investigational agent and received study therapy or used an investigational device within 4 weeks of the first dose of treatment.
5. Has a diagnosis of immunodeficiency or is receiving systemic steroid therapy or any other form of immunosuppressive therapy within 7 days prior to the first dose of trial treatment.
6. Has a known history of active TB (Bacillus Tuberculosis)
7. Hypersensitivity to pembrolizumab or any of its excipients.
8. Has had a prior anti-cancer monoclonal antibody (mAb) within 4 weeks prior to study Day 1 or who has not recovered (i.e.,  $\leq$  Grade 1 or at baseline) from adverse events due to agents administered more than 4 weeks earlier.
9. Has had prior chemotherapy, targeted small molecule therapy, or radiation therapy within 2 weeks prior to study Day 1 or who has not recovered (i.e.,  $\leq$  Grade 1 or at baseline) from adverse events due to a previously administered agent.
  - Note: Subjects with  $\leq$  Grade 2 neuropathy are an exception to this criterion and may qualify for the study.
  - Note: If subject received major surgery, they must have recovered adequately from the toxicity and/or complications from the intervention prior to starting therapy.
10. Has a known additional malignancy that is progressing or requires active treatment within the past 3 years. Exceptions include basal cell carcinoma of the skin or squamous cell carcinoma of the skin that has undergone potentially curative therapy or *in situ* cervical cancer.
- .

11. Has known active central nervous system (CNS) lymphoma or lymphomatous meningitis. Subjects with previously treated brain metastases may participate provided they are stable (without evidence of progression by imaging for at least four weeks prior to the first dose of trial treatment and any neurologic symptoms have returned to baseline), have no evidence of new or enlarging brain metastases, and are not using steroids for at least 7 days prior to trial treatment.
12. Has active autoimmune disease that has required systemic treatment in the past 2 years (i.e. with use of disease modifying agents, corticosteroids or immunosuppressive drugs). Replacement therapy (eg., thyroxine, insulin, or physiologic corticosteroid replacement therapy for adrenal or pituitary insufficiency, etc.) is not considered a form of systemic treatment.
13. Has history of (non-infectious) pneumonitis that required steroids, evidence of interstitial lung disease or active, non-infectious pneumonitis.
14. Has an active infection requiring systemic therapy.
15. Has a history or current evidence of any condition, therapy, or laboratory abnormality that might confound the results of the trial, interfere with the subject's participation for the full duration of the trial, or is not in the best interest of the subject to participate, in the opinion of the treating investigator.
16. Has known psychiatric or substance abuse disorders that would interfere with cooperation with the requirements of the trial.
17. Is pregnant or breastfeeding, or expecting to conceive or father children within the projected duration of the trial, starting with the pre-screening or screening visit through 120 days after the last dose of trial treatment.
18. A WOCBP who has a positive urine pregnancy test within 72 hours prior to receiving the first dose of study medication (see Appendix 3). If the urine test is positive or cannot be confirmed as negative, a serum pregnancy test will be required.

*Note: in the event that 72 hours have elapsed between the screening pregnancy test and the first dose of study treatment, another pregnancy test (urine or serum) must be performed and must be negative in order for subject to start receiving study medication.*

19. Has received prior therapy with an anti-PD-1, anti-PD-L1, or anti-PD-L2 agent directed to another stimulatory or co-inhibitory T-cell receptor (eg, CTLA-4, OX-40, CD137).
20. Has a known history of Human Immunodeficiency Virus (HIV) (HIV 1/2 antibodies).
21. Has known active Hepatitis B (e.g., HBsAg reactive) or Hepatitis C (e.g., HCV RNA [qualitative] is detected).
22. Has received a live vaccine within 30 days of planned start of study therapy.

*Note: Seasonal influenza vaccines for injection are generally inactivated flu vaccines and are allowed; however intranasal influenza vaccines (e.g., Flu-Mist®) are live attenuated vaccines, and are not allowed.*

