## 1.0 TRIAL SUMMARY

Abbreviated Title	Pembrolizumab (MK-3475) and radiation for relapsed and refractory Non-Hodgkin Lymphoma
Trial Phase	II
Clinical Indication	Refractory Non-Hodgkin Lymphoma
Trial Type	Treatment (Interventional)
Type of control	Historical Control
Route of administration	Intravenous and external beam radiation
Trial Blinding	Unblinded, open label
Treatment Groups	MK-3475 200 mg every 21 days with concurrent External beam radiation therapy (EBRT)
Number of trial subjects	21
Estimated enrollment period	20 months
Estimated duration of trial	48 months
Duration of Participation	1.5 years
Estimated average length of treatment per patient	24 months

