It is likely that the timing of immune checkpoint blockade and EBRT influence the effectiveness of therapy. In a pre-clinical model of melanoma, breast and colorectal cancer, the anti-tumor activity of low dose fractionated RT was enhanced through the combination of a monoclonal antibody targeting PD-L1. In this mouse model, treatment timing and scheduling was significantly affected treatment efficacy; with concurrent RT and PD-L1 therapy but not sequential therapy resulting in beneficial local control and survival. Based on these data we propose that pembrolizumab and fractionated RT should be administered concurrently.

The overall response rates of refractory NHL to single modality radiation therapy are relatively high but often not durable. In a retrospective study from the Dana-Farber Cancer Institute of 110 patients treated with a course of salvage radiation therapy for relapsed or refractory aggressive NHL, the overall response rate was 78% among refractory patients treated with curative intent and 81% for those refractory patients treated with palliative intent. Among living patients the 5 year rate of progression free survival however was only 34%. Furthermore even among patients treated with doses greater than 40 Gy with curative intent the 2 year local control rate was only 61%. This highlights 1) the need for effective systemic therapies to pair with salvage radiation therapy and 2) the room for improvement in long term local control that for patients with refractory NHL that may be accomplished with concurrent systemic therapy.

Given this data this study will address the role of pembrolizumab and concurrent RT in two patient populations. The first eligible cohort will include patients with more disseminated disease where all disease will not be included in the radiation field and there will be an “unirradiated lesion”. The second cohort of eligible patients will be those with relapsed/refractory aggressive NHL where all sites of disease can be encompassed in 1-2 radiation therapy fields. We hypothesize that 1) the response rates of the unirradiated lesion will be higher than reported ORR among patients treated previously with PD-1 blockade monotherapy for relapsed and refractory NHL and 2) the response rates for patients treated

with pembrolizumab and RT fields encompassing all sites of disease will be also be improved over rates reported for salvage RT alone.

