### **8.0 STATISTICAL ANALYSIS PLAN**

#### **8.1 Statistical Analysis Plan Summary**

This is an investigator initiated, open label, phase II clinical trial to evaluate the efficacy of the combination therapy of Pembrolizumab and fractionated external beam radiotherapy (EBRT) in patients with relapsed and refractory aggressive Non-Hodgkin lymphoma (NHL). The maximum number of patients that will be recruited for the study is 40.

The primary objective of the trial is to determine the overall response rate of Pembrolizumab and fractionated EBRT in patients with relapsed and refractory NHL. The secondary objectives are to evaluate the safety, CRR, PFS, OS and duration of response of pembrolizumab with concurrent fractionated EBRT. Patients will receive 200 mg IV of Pembrolizumab with concurrent EBRT at standard of care doses of 40-50 Gy of EBRT in fractions of  $\leq 3$  Gy.. The trial enrollment will be stratified according to the extent of relapsed/refractory disease included in the RT field(s) with 2 cohorts of patients enrolled based on the treated RT field. For Cohort 1, patients with aggressive NHL, will receive RT to 1-2 region(s) of disease and the ORR will be determined for a designated “unirradiated” lesion (Cohort 1). For patients with relapsed/refractory aggressive NHL in Cohort 2, RT will be administered to encompass all sites of radiographically evident disease in 1-2 RT plan(s), the ORR will be based on the disease treated within the RT field. **The maximum number of patients in each cohort is 20 with a total anticipated trial enrollment of 40 patients..**

Overall response rates to PD-1 blockade monotherapy among patients with hematologic malignancies is based on published data. For cohort 1, we assume that concurrent external beam radiation therapy with concurrent pembrolizumab will improve ORR (of the non-irradiated lesion[s]) over the reported rates of PD-1 blockade which are roughly 26% for B cell lymphoma and 17% for T cell lymphoma.

**While the ORR for definitive RT for patients with de novo aggressive NHL approach 100%, overall response rate to salvage RT for patients with refractory aggressive NHL treated with curative intent has been reported to be 78%, with a 5 year progression free survival rate of 34%. We assume that concurrent EBRT and pembrolizumab will improve the ORR when all sites of known disease are radiated.**

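### Exclusion 19 is missing words, so no explicit rule clearly bars patients already treated with a PD-1-axis agent or another checkpoint-directed agent

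*Combined protocol and SAP*

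**What the plan says.** Exclusion 19 in Section 5.1.3 applies to a patient who "Has received prior therapy with an anti-PD-1, anti-PD-L1, or anti-PD-L2 agent directed to another stimulatory or co-inhibitory T-cell receptor"; CTLA-4, OX-40 and CD137 follow as examples. The sentence runs on without a gap or redaction mark.

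Three other exclusions in the same section touch prior therapy of this kind:

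- Exclusion 8: "Has had a prior anti-cancer monoclonal antibody (mAb) within 4 weeks prior to study Day 1", or incomplete recovery from the adverse events of agents given earlier than that.
- Exclusion 4: current participation, or past participation in a study of "an investigational agent and received study therapy or used an investigational device within 4 weeks of the first dose of treatment".
- Exclusion 15: "Has a history or current evidence of any condition, therapy, or laboratory abnormality that might confound the results of the trial", qualified by the treating investigator's opinion.

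The inclusion criteria in Section 5.1.2 do not restrict the type of prior systemic therapy.

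Section 1.0 gives the type of control as "Historical Control". Section 4.2.1 hypothesises that "the response rates of the unirradiated lesion will be higher than reported ORR among patients treated previously with PD-1 blockade monotherapy". Section 8.1 assumes that the combination "will improve ORR (of the non-irradiated lesion[s]) over the reported rates of PD-1 blockade", which it puts at roughly 26% for B-cell and 17% for T-cell lymphoma. Section 8.2 calls the cohort 1 regimen promising if the 3-month response rate of the non-irradiated lesion(s) is at least 35%. It stops the cohort after 10 patients if 0 or 1 have responded.

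**The concern.** In exclusion 19 a single noun, *agent*, carries two descriptions, and no conjunction separates them. Taken at its word, the criterion needs an agent that targets the PD-1 axis and is also directed to some other T-cell receptor. An ordinary anti-PD-1 antibody fails the second condition. An ordinary CTLA-4, OX-40 or CD137 antibody fails the first. The text therefore does not clearly bar either group.

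With historical control, comparability with the benchmark rests on who is let in. Cohort 1 asks whether radiation adds to PD-1 blockade. Patients who have already had PD-1 blockade bring in a different question, namely re-treatment after exposure. If they respond less often, the cohort 1 rate falls, and an early futility stop becomes more likely for a reason unrelated to any contribution from radiation.

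**Working it through.** **Does another rule close the gap?** Take a hypothetical patient whose last anti-PD-1 dose was five weeks before Day 1 and who has recovered from toxicity.

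| Criterion (Section 5.1.3) | Effect on this patient |
|---|---|
| 19, literal reading | Not met: the agent is not directed to another receptor |
| 19, with an *or* supplied | Met: excluded |
| 8 | Not met: outside 4 weeks, recovered |
| 4 | Not met: outside 4 weeks, if the agent was investigational |
| 15 | Depends on the investigator's opinion; checkpoint agents are not named |

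No explicit rule excludes this patient. Only the intended reading of 19 or a judgement under 15 does so.

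**The plan's own figures (Section 8.2, cohort 1).** Inputs: prior Beta(0.35, 0.65), a look at n = 10, stop if P(response rate < 0.35 | data) > 0.95.

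- 1 response in 10: posterior Beta(1.35, 9.65), probability 0.971, so stop.
- 2 responses in 10: posterior Beta(2.35, 8.65), probability 0.865, so continue. The 0-1 boundary reproduces.
- Futility stop at a true rate of 0.35: 0.65^10 + 10 × 0.35 × 0.65^9 = 0.0135 + 0.0725 = 0.0860.
- Either stop, with a true DLT rate of 0.1: 1 − (1 − 0.0860) × P(at most 5 DLTs in 10) = 0.0861, the tabulated value.
- 90% credible interval width at 7/20, from Beta(7.35, 13.65): 0.3346, against 0.335 stated.

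The point disputes none of these figures.

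**Illustration of size.** The documents give neither the share of pretreated patients nor their response rate, so both are assumptions: share f from 0 to 20%, response r from 0 to 20%. All other patients are taken to respond at the 35% target.

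- Mixed rate: m = 0.35(1 − f) + r f.
- Futility stop: (1 − m)^10 + 10 m (1 − m)^9.
- Last column: chance of passing the look and reaching at least 7/20 (an observed 35%), which is the sum over a = 2 to 10 of P(a of the first 10) × P(at least 7 − a of the next 10).

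| f | r | m | Futility stop at 10 | Pass and ≥ 7/20 |
|---|---|---|---|---|
| 0 | – | 35.0% | 8.6% | 57.6% |
| 10% | 0 | 31.5% | 12.7% | 44.3% |
| 10% | 10% | 32.5% | 11.4% | 48.2% |
| 10% | 20% | 33.5% | 10.2% | 52.0% |
| 20% | 0 | 28.0% | 18.3% | 31.2% |
| 20% | 10% | 30.0% | 14.9% | 38.6% |
| 20% | 20% | 32.0% | 12.1% | 46.3% |

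Fixing the count at exactly 2 pretreated patients in the first 10, rather than 20% on average, gives a futility stop of 16.9%, 14.3% and 11.8% for r = 0, 10% and 20%. The picture is the same.

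**The case against.** The strongest reply is that nobody would apply the literal reading. It would exclude almost no one. The criterion opens with three PD-1-axis classes, and the word *another*, with its own list of examples, signals a second class. Supplying an *or* excludes both. The trial is single-center, so different sites cannot diverge in how they read it, and exclusion 15 lets the investigator turn away a patient whose prior therapy would confound the results. Much of this stands: the fault is probably in drafting, not in design. It does not remove the point, because an eligibility rule has to be auditable as written, and exclusion 15 is discretionary.

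Three stronger conclusions are tempting, and the documents do not support them.

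- A reader might infer that pretreated patients are positively eligible, with exclusion 8 as the only other safeguard. Exclusions 4 and 15 also bear on them, and the apparent intent of 19 is to exclude them.
- A reader might infer that the comparison with PD-1 monotherapy is undermined. That requires pretreated patients to have been enrolled, and the documents do not show that any were. Section 4.2.1 also does not state the prior checkpoint exposure of the historical series. If pretreated patients respond less often, the bias lowers the observed rate, so it could not create a false appearance of benefit.
- A reader might take the percentages above as an estimate of harm. They rest on assumed shares and response rates, and with no pretreated patients the effect is nil.

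The PD-1 benchmark concerns cohort 1 only. Cohort 2 is set against salvage radiation at 78%, although exclusion 19 applies to both cohorts.

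**Conclusion.** The wording defect is real and sits in an operative eligibility rule. As printed, exclusion 19 does not clearly bar prior PD-1-axis therapy or prior therapy directed to other T-cell receptors, and no other explicit criterion does so, although both exclusions were probably meant.

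The consequence is conditional: a downward bias in the cohort 1 response rate if pretreated patients enrol and respond less often than the rest. On the stated assumptions the interim futility stop rises from 8.6% to about 10-13% at 10% pretreated and 12-18% at 20% pretreated. The wording should be corrected; the statistical design does not need to be reopened.

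**What to change.** Restate exclusion 19 as two separate criteria: one for any prior anti-PD-1, anti-PD-L1 or anti-PD-L2 agent, and one for any prior agent aimed at a different co-stimulatory or inhibitory receptor on T cells, keeping the existing examples. The sponsor should confirm that this is the intended scope. Check patients already enrolled for prior checkpoint therapy, and report the responses of any such patients separately.

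The cost is a short amendment and a review of treatment histories. Accrual loses nothing if the intended rule is already being applied. Sample size, stopping boundaries and operating characteristics stay as they are.
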